13.14 PREMATURE STUDY TERMINATION (*Discontinuation of Entire Study*)

Both the sponsor and the investigator reserve the right to terminate the study according to the study contract. The sponsor has the right to terminate the trial prematurely if there are any relevant medical or ethical concerns, or if completing the trial is no longer practicable. The sponsor decides on whether to discontinue the trial in consultation with IDMC.

If such action is taken, the reasons for terminating the trial must be documented in detail in the trial master file. The sponsor will inform the IEC/IRB and the competent authorities in writing of the study's completion or early termination at the time and send a copy of the notification to all investigators.

Premature termination of the trial will be considered if:

- The risk-benefit balance for the trial subject changes markedly
- It is no longer ethical to continue treatment with the IMP
- The sponsor considers that the trial must be discontinued for safety reasons

- It is no longer practicable to complete the trial

If the investigator decides a termination of a single subject or has any ethical concerns about continuation of the trial, the investigator must inform the sponsor. All information about the termination must be documented in the investigator site file. All trial subjects still under treatment at the time of termination must undergo a final examination which must be documented.

13.15 Continuation of treatment after the end of trial

After conclusion of the clinical trial, patients will receive further standard medical care as usual for this kind of disease.

13.17 Study Stopping Rules

Study Stopping Rules in the phase I

The dose limiting toxicities (DLT) observation period is defined as the first treatment cycle (Cycle 1) of venetoclax combined with azacitidine.

Dose limiting toxicities for dose escalation purposes will be determined based on adverse events that occur during the DLT observation period.

Adverse events occurring after the DLT observation period criteria will also be reviewed and may be taken into consideration for dose escalation decisions.

Any of the following events will be considered a DLT unless the event can be attributed by the investigator to a clearly identifiable cause such as underlying illness or disease progression, concurrent other illness, or concomitant medication:

- ANC $< 1 \times 10^9/L$ (Grade ≥ 3) which does not recover as defined below:
 - o Recovery is defined as an increase in ANC from nadir by $\geq 50\%$ of the reduction from baseline to nadir or any increase to an ANC of $\geq 1 \times 10^9/L$ within 42 days from Day 1 of Cycle 1
 - o Delayed recovery should only be deemed a DLT if due to treatment induced toxicity as confirmed by a bone marrow sample showing an overall bone marrow cellularity of $< 5\%$
- Grade ≥ 3 thrombocytopenia associated with clinically significant bleeding that requires transfusion of platelets over routine or baseline transfusion needs based on investigator opinion
- Grade ≥ 4 non-hematologic toxicity deemed related to venetoclax per investigator opinion.
- Grade 4 infections or complications related to infections (e.g., sepsis) should only be deemed DLTs if due to treatment-induced neutropenia as confirmed by a bone marrow sample showing an overall bone marrow cellularity of $< 5\%$

Occurrence of a DLT event will require an interruption and possible discontinuation of study treatment administration to the patient that experienced the DLT. All decisions regarding continued dosing for individual subjects will be medically managed by the investigator, per discussion with the GFM, as appropriate. These decisions will be driven by the definition of DLTs as described above.

In addition, any treatment related death will be reported to the safety committee within 24 hours, the safety committee will review, discuss and provide guidance to the sponsor according to the safety committee charter.

Study Stopping Rules in the phase II

Any of the following events will be considered a DLT unless the event can be attributed by the investigator to a clearly identifiable cause such as underlying illness or disease progression, concurrent other illness, or concomitant medication:

- ANC $< 1 \times 10^9/L$ (Grade ≥ 3) which does not recover as defined below:

- Recovery is defined an increase in ANC from nadir by $\geq 50\%$ of the reduction from baseline to nadir or any increase to an ANC of $\geq 1 \times 10^9/L$ within 42 days from Day 1 of Cycle 1
- Delayed recovery should only be deemed a DLT if due to treatment induced toxicity as confirmed by a bone marrow sample showing an overall bone marrow cellularity of $< 5\%$
- Grade ≥ 3 thrombocytopenia associated with clinically significant bleeding that requires transfusion of platelets over routine or baseline transfusion needs based on investigator opinion
- Grade ≥ 4 non-hematologic toxicity deemed related to venetoclax per investigator opinion.
- Grade 4 infections or complications related to infections (e.g., sepsis) should only be deemed DLTs if due to treatment-induced neutropenia as confirmed by a bone marrow sample showing an overall bone marrow cellularity of $< 5\%$

We will stop the enrollment of new patients at the request of the DSMB if DLT attributable to VEN > 2 . Ongoing patients without toxicities and with a benefit of treatment at the investigator's discretion will be allowed to continue to receive treatment according to the protocol.

13.18 Study Safety Committee

An independent Data Monitoring Committee/Data Safety Monitoring Board (DMC/DSMB) will be formed to oversee the safety of the study subjects by periodically assessing the safety of the study therapy. The DSMB will consist of three physicians who are not involved in the study and who are external to the sponsor. The study DSMB charter will elaborate the guidelines for the DSMB. Subsequently the DSMB will meet according to the intervals mentioned in the DSMB Charter.

The Safety Committee recommendations will be binding and the sponsor commits to promptly implement any safety recommendations related to changes to the eligibility criteria, dose adjustments and study discontinuation.

14 QUALITY ASSURANCE

In order to guarantee the authenticity and credibility of the data in accordance with Good Clinical Practice (GCP), the sponsor shall put in place a quality assurance system which includes:

- Management of the trial in accordance with GFM's procedures,
- Quality control of the investigator site data by the monitor, whose role is to check the data in the case report form for concordance and consistency with the source documents,
- The possible audit of investigator sites.

15 OWNERSHIP OF THE DATA AND CONFIDENTIALITY

The investigator undertakes that he/she and anyone who monitors the conduct of the trial will ensure the confidentiality of all of the information provided by GFM until the trial results are published. This confidentiality requirement shall not apply to information that the investigator gives to patients in connection with their participation in the trial or to previously published information.

The investigator undertakes not to publish, disclose, or use any trial-related scientific or technical information, in any way, either directly or indirectly.

Nevertheless, in accordance with Article R 5121-13 of the French public health code, the site and the investigator can give information about the trial:

- To the minister for health,
- To public health inspectors (medical doctors or pharmacists),
- To the General Director and inspectors of the ANSM.

No written or verbal comments can be made about the trial without the sponsor's consent, since all of the information provided or obtained while the trial is being conducted legally belongs to the sponsor, which can use the information at its own discretion.

16 PUBLICATION POLICY

All of the information arising from this trial shall be considered confidential, at least until completion of the appropriate analysis and subsequent checks by the trial sponsor, coordinating investigator, and statistician.

Any publications, abstracts or presentations that include results from the trial must be submitted to the sponsor for approval.

Any communications, articles, or presentations must also include a section mentioning the GFM and the organizations that supported the research financially.

The trial's coordinating investigator will be the main (first or last) author.

The first or last author (depending on the position given to the coordinating investigator) will be jointly selected by the sponsor and the coordinating investigator (CI).

The following investigators will be cited in order of the number of patients recruited for multicenter trials, or based on their involvement in the protocol and/or the disease. The trial statistician will also be cited.

Similarly, publications of ancillary results (biological studies) shall include the name of the person who carried out the ancillary study, as well as the names of anyone else involved in the ancillary study.

17 ETHICAL AND REGULATORY ASPECTS

The clinical trial must be conducted in accordance with:

- The ethical principles of the current version of the Declaration of Helsinki,
- The guideline for Good Clinical Practice of the International Conference on Harmonization (ICH–E6, 07/17/96),
- European Directive 2001/20/EC on the conduct of clinical trials,
- The French Huriet Act (No. 88-1138) dated December 20, 1988 concerning the protection of clinical trial subjects, amended by the French public health law No. 2004-806 dated August 09, 2004,
- The French data protection and civil liberties law No. 78-17 dated January 06, 1978, amended by law 2004-801 of August 06, 2004 regarding the processing of personal data,
- French law No. 2004-800 dated August 06, 2004 concerning bioethics.

17.1 Research Ethics Board

Before conducting biomedical research on human subjects, the sponsor is obliged to submit the project to one of the REBs for its opinion.

The sponsor also submits applications for substantial amendments to the initial project to the REB for its opinion.

17.2 Competent Authority

Before conducting a clinical trial or having one conducted, the sponsor of the trial shall apply to the ANSM for authorization.

17.3 Subject information and consent

Before biomedical research is conducted on a person, their voluntary, written, informed consent must be obtained, after they have been fully informed by the investigator during a consultation and given enough time to consider their decision.

Information intended for trial subjects must include all of the particulars set out in the French public health law of August 09, 2004 and must be written in straightforward language that the patient can understand.

The consent form must be signed and dated personally by the trial subject and the investigator (the original copy shall be archived by the investigator, and one copy will be given to the trial subject).

The patient information leaflet and informed consent form must be combined into a single document to ensure that all of the information is given to the trial subject.

17.4 Responsibilities of the sponsor

The sponsor of the clinical trial is the individual or legal entity that takes the initiative for the biomedical research on human subjects, manages the trial, and ensures that provision has been made for its funding.

The sponsor must be established in the European Community or, failing that, have a legal representative in a member state.

The sponsor's main responsibilities are to:

- Take out civil liability insurance,
- Register the trial in the European trials database and obtain the EudraCT number (European Drug Regulatory Authorities Clinical Trials),
- Request the opinion of the REB on the initial project and substantial amendments,
- Request authorization for the initial project and substantial amendments from the competent authority,
- Provide information about the trial to the site directors, investigators, and pharmacists,
- Report any suspected unexpected serious adverse events related to any of the trial treatments to the competent authority, ANSM and EMEA (European pharmacovigilance database, Eudravigilance), and send this information to the REB and the trial investigators,
- Submit the annual safety report to the competent authority and the REB,
- Notify the competent authority of the start and end of the trial,
- Write the final clinical study report,
- Send the trial results to the competent authority, REB, and trial subjects,

- Archive essential trial documents in the sponsor's folder for a minimum of 15 years after the trial has ended.

17.5 Responsibilities of investigators

The principal investigator of each establishment concerned undertakes to conduct the clinical trial in accordance with the protocol approved by the REB and the competent authority.

The investigator must not make any changes to the protocol without the written authorization of the sponsor and unless the REB and the competent authority have approved the proposed changes.

It is the responsibility of the principal investigator to:

- Provide the sponsor with his/her curriculum vitae as well as those of his/her co-investigators, identify the members of his/her team, who are participating in the trial and define their responsibilities,
- Recruit patients once authorized to do so by the sponsor.

It is the responsibility of each investigator to:

- Obtain informed consent, personally signed and dated by the subject, before carrying out any trial-specific screening procedures,
- Regularly complete the case report form (CRF) of each patient enrolled in the trial and allow the clinical research assistant (CRA) appointed by the sponsor to have direct access to source documents, so that the latter can validate the data on the CRF,
- Date, correct, and sign corrections on the CRF of each patient enrolled in the trial,
- Accept regular visits by the monitor, and any auditors appointed by the sponsor or inspectors from the regulatory authorities.

All of the trial-related documentation (the protocol, consent forms, case report forms, investigator brochure, etc.) and source documents (laboratory results, X-rays, consultation reports, physical exam reports, etc.) are considered confidential and must be kept in a safe place. The principal investigator must store the data and a patient identification list for a minimum of 15 years after the end of the study.

18 INSURANCE

In accordance with current legislation, insurance has been taken out with the company CHUBB European Group SE contract N° FRLCSA61513 to cover any physical harm or other incapacity that may result from administration of the investigational treatment, in accordance with the study protocol.

19 PROTOCOL DEVIATIONS

When an emergency occurs that requires a deviation from the protocol for a subject, a deviation will be made only for that subject. A decision will be made as soon as possible to determine whether or not the subject (for whom the deviation from protocol was effected) is to continue in the study. The subject's medical records will completely describe the deviation from the protocol and state the reasons for such deviation.

20 SUBJECT CONFIDENTIALITY

The Sponsor affirms the subject's right to protection against invasion of privacy in compliance with the local legal practice.

All records identifying the subject will be kept confidential and, to the extent permitted by the applicable laws and / or regulations, will not be made publicly available.

Subject names will not be supplied to the Sponsor. Only the subject number will be recorded in the CRF, and if the subject name appears on any other document (e.g., pathologist report), it must be obliterated before a copy of the document is supplied to the Sponsor. Study findings stored on a computer will be stored in accordance with local data protection laws. The subjects will be informed in writing that representatives of the Sponsor, IEC / IRB, or regulatory authorities may inspect their medical records to verify the information collected, and that all personal information made available for inspection will be handled in strict confidence and in accordance with local data protection laws.

If the results of the study are published, the subject's identity will remain confidential.

The investigator will maintain a list to enable subjects to be identified.

21 ARCHIVING

All documents, informed consent forms and other important study materials will be archived for at least 15 years.

Essential documents shall be archived in such a way that ensures that they are readily available upon authorities' request.

Patient (hospital) files will be archived according to local regulations and in accordance with the maximum period of time permitted by the institution. Where the archiving procedures do not meet the minimum timelines required by the Sponsor, alternative arrangements must be made to ensure the availability of the source documents for the required period.

The investigator/institution notifies the Sponsor if the archival arrangements change (e.g. relocation or transfer of ownership). The ISF is not to be destroyed without the Sponsor's approval. The investigator's contract will contain all regulations relevant for the study center.

22 AMENDMENTS TO THE STUDY PROTOCOL

To ensure that comparable conditions are achieved as far as possible at individual study sites and in the interests of a consistent and valid data analysis, changes to the provisions of this study protocol are not planned. In exceptional cases, however, changes may be made to the study protocol. Such changes can only be made if agreed by the Sponsor, Sponsor's representative and all authors of this study protocol. Any changes to the study procedures must be made in writing and must be documented with reasons and signed by all authors of the original study protocol.

Amendments made in accordance with GCP Regulations that require approval are submitted to the ethics committee and the supreme federal authority and will not be implemented until approved. Exceptions to this are amendments made to avoid immediate dangers.

24 APPENDIX

24.1 Appendix 1: VISIT SCHEDULE

	Screening ^a	Cycle 1					Cycle 2 and above ^b					End of Study ^c
Day	(-14 to 0)	1	7	15	21	28	1	7	15	21	28	
Visit	1	2	3	4	5	6	7	8	9	10	11	Final
Informed consent	X											
Demography and medical history	X											
Prior/concomitant medications ^d	X	X	X	X	X	X	X		X		X	X
Review inclusion/exclusion criteria	X											
Height/weight/body surface area calculation	X	X					X					X
Vital signs ^e	X	X	X	X	X	X	X		X			X
Physical examination ^f	X	X		X			X					X
ECOG performance status ^g	X	X		X			X					X
12-lead ECG	X			X			X					
CBC w/diff, platelets ^h	X	X	X	X	X	X	X	X	X	X	X	X
Comprehensive chemistry panel ⁱ	X	X	X	X	X	X	X		X		X	X
PT (INR) PTT	X	X					X					X
Complete urinalysis with microscopic exam	X											
Pregnancy Test ^j (if applicable)	X						X					
T/B/NK phenotype and Centralized biology	X						X				X ^l	X
Blood chimerism (CD3 sorted)	X						X					X
Medullar chimerism ^k	X										X	X
Adverse experience (AE) assessment		X	X	X	X	X	X		X		X	X
Dispense AZA		X					X					
Dispense VENETOCLAX		X					X					
Bone marrow aspirate /cytogenetics and for correlative studies ^l	X										X ^l	X

- a All pre-treatment studies should be obtained within 14 days of entry into the trial. Any abnormal results (except for bone marrow aspiration) should be repeated within 48 hours of beginning therapy to establish a baseline.
- b Patients may receive additional Cycles of therapy but not earlier than 4 weeks from the previous Cycle. One full cycle of treatment is defined as the administration of AZA and VENETOCLAX. During additional Cycles, patient Visits are numbered sequentially.
- c To be completed within 30 days of discontinuing study drug.
- d Medications will include the RBC and Platelet transfusions charts for the 8 weeks preceding inclusion and for the 8 weeks preceding beginning of AZA.
- e Vital signs to include temperature, pulse, respiratory rate and blood pressure.
- f A complete history and physical should be performed 48 hours before initiation of the study. A focused physical exam based on clinical assessment and AE evaluation should be conducted prior to the start of each Cycle.
- g See Appendix 5. ECOG should be performed within 48 hours of study initiation and then at the start of each Cycle.
- h CBC w/diff and platelet count should be completed weekly for the first 2 Cycles and then at the start of each subsequent Cycle. A sample collected on day 28 does not need to be repeated on day 1 of the next Cycle if the 2 Visits are within 72 hours of each other.
- i Complete chemistry panels should be performed within 48 hours of study initiation and then weekly in the Cycle 1 and 2, and bi-weekly at the start of each subsequent Cycle. A sample collected on Day 28 does not need to be repeated on Day 1 of the next Cycle if the 2 Visits are within 72 hours of each other. The panel includes sodium, potassium, chloride, carbon dioxide, BUN, creatinine, magnesium, calcium, phosphorus, glucose, total protein, albumin, AST, ALT, uric acid, lactate dehydrogenase (LDH), alkaline phosphatase and total/direct bilirubin at the beginning of each Cycle.
- j Female subjects of childbearing potential must have negative results for pregnancy test performed at Screening with a serum sample obtained within 14 days prior to the first study drug administration, and prior to dosing with urine sample obtained on Cycle 1 Day 1, if it has been > 7 days since obtaining the serum pregnancy test results. Female subjects who are not of childbearing potential at Screening do not require pregnancy testing.
- k Every 2 cycles.
- l Bone marrow aspiration (BMA) should be conducted prior to study initiation and then after 4, 6 and 8 cycles of AZA + VENETOCLAX and at the end of study or Premature termination. BMA collected on Day 0 of cycle 1 will be for correlative, morphologic and cytogenetic sampling. The other BMA will be for response assessment. Cytogenetics should be repeated in case of abnormal findings at baseline.

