8.7 Follow-Up

Follow-up after treatment discontinuation for all patients.

Patients will be followed at 3 months and 6 months after treatment discontinuation. Date of death or last follow-up, disease status, and ongoing hematological treatments will be collected.

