8.11 Safety Assessments

Safety assessments will be based on changes from baseline of AEs reported by the patients or observed by the Investigator, concomitant medication and blood product use, treatment discontinuation due to AEs, vital signs, ECG, physical examination, laboratory assessments (hematology, blood chemistry), and evaluation of the performance status by the ECOG.

AEs and SAEs will be graded according to the CTCAE, version 5. All AEs (serious and non-serious) occurring between Study Day 1 and 30 days following the last dose of study treatment of each course will be documented in the trial subject's medical records. The following AEs will additionally be documented in the eCRF if:

- Serious (SAE) as defined in 13.2, whether or not related to study drug,
- Related to study drug, regardless of grade and clinical significance,
- Unrelated to study drug but grade ≥ 3 and clinically significant.

AEs and SAEs occurring after 30 days of the last study treatment dose in each course, should only be recorded if considered at least possibly related to study treatment by the local investigator. SAEs and Grade 3 or higher AEs that are ongoing at the end of this period (30 days from last study treatment administration) will be followed until each event is resolved or is assessed as chronic. Serious and nonserious adverse events occurring after the study-specific informed consent is signed but prior to Study Day 1 will be collected only if they are considered by the investigator to be causally related to the study-required procedures.

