13 SAFETY AND PHARMACOVIGILANCE

13.1 Adverse Event

An AE is defined as any unintended sign (including an abnormal laboratory finding), symptom, or disease temporally associated with the use of an investigational medicinal product, whether or not considered related to the investigational medicinal product.

In this study, any event occurring after the Study Day 1 and within 30 days of the last study treatment dose of each course should be recorded and reported as an AE. AEs and SAEs occurring after 30 days should only be recorded if considered at least possibly related to study treatment by the local Investigator. Serious and non-serious adverse events occurring after the study-specific informed consent is signed but prior to Study Day 1 will be collected only if they are considered by the investigator to be causally related to the study-required procedures

Laboratory values related to AML, HR MDS and AML, HR MDS progression such as anemia, neutropenia, thrombocytopenia, should not be classified as AEs as long as they are within the expected progression of the disease or expected duration/severity.

The reporting of abnormal laboratory values from unscheduled tests should be avoided unless they lead to clinical consequences or are associated with an AE.

AEs occurring during the study, whether or not attributable to the study treatment, observed by the investigator or reported by the patient spontaneously or in response to a direct question, will be recorded in the patient's source documents as long as they occurred during study treatment administration or within 30 days of last study treatment dose of each course. AEs occurring after 30 days should only be recorded if considered at least possibly related to study treatment by the local Investigator. AEs will be graded in accordance with NCI CTCAE version 5.

For adverse events not captured by the Common Terminology Criteria, the following should be used:

Grade 1: The adverse event is transient and easily tolerated by the subject (mild).

Grade 2: The adverse event causes the subject discomfort and interrupts the subject's usual activities (moderate).

Grade 3: The adverse event causes considerable interference with the subject's usual activities and may be incapacitating (moderate to severe).

Grade 4: The adverse event is life threatening requiring urgent intervention (severe).

Grade 5: The adverse event resulted in death of the subject (severe).

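### The last scheduled adverse-event assessment may fall before the 30-day adverse-event window closes, and no later scheduled contact is listed to cover the remainder

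*Protocol*

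**What the plan says.** **AE window.** Protocol section 8.11 covers "All AEs (serious and non-serious) occurring between Study Day 1 and 30 days following the last dose of study treatment of each course". Section 13.1 sets the same end: an event "within 30 days of the last study treatment dose of each course should be recorded and reported as an AE". Section 13.2 gives SAEs the same 30-day limit. Beyond day 30, an event "should only be recorded if considered at least possibly related to study treatment by the local investigator".

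**Visits.** In Appendix 1 the row "Adverse experience (AE) assessment" is ticked at days 1, 7, 15, 21 and 28 of Cycle 1, at days 1, 15 and 28 of later cycles, and at End of Study, which is the last column. Footnote c times that visit: "To be completed within 30 days of discontinuing study drug".

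**After End of Study.** Section 8.7 states: "Patients will be followed at 3 months and 6 months after treatment discontinuation". It lists what is gathered: "Date of death or last follow-up, disease status, and ongoing hematological treatments will be collected". AEs are not on the list.

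**The concern.** The window has a fixed end, but the visit that should close it has only a latest date. A site that holds the End of Study visit soon after stopping has followed the protocol, yet nobody is scheduled to ask about AEs for the rest of the 30 days.

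Section 8.11 also requires follow-up of "SAEs and Grade 3 or higher AEs that are ongoing at the end of this period". That presupposes the patient's status at day 30 is known, and no scheduled contact establishes it.

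At stake is the completeness of the safety data after the final course. Section 13.13 ends treatment for, among other reasons, unacceptable AEs, grade 4 toxicity, persistent myelosuppression and progression, so post-treatment events are to be expected in some of these patients. Toxicity profile is the phase I primary endpoint (5.1), toxicity is a secondary endpoint (5.2), and infections are events of special interest (9.2).

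**Working it through.** The plan states no figure on this point, so there is none to reproduce. The check is calendar arithmetic.

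**Inputs**
- Window end: day 30 after the last dose (8.11, 13.1, 13.2).
- End of Study visit: latest day 30 after discontinuing study drug, with no earliest day (Appendix 1, footnote c).
- Next contact: 3 months, AEs not listed (8.7).
- Last venetoclax day in a cycle: day 14 (6.1).
- DLI: day 15 of cycles 2, 4, 6 and 8 (6.1).

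**Formula.** Days without a scheduled AE assessment = max(0, 30 − d), where d is the day of the last scheduled AE assessment counted from the last dose.

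| End of Study visit, days after last dose | Days of window left open |
|---|---|
| 0 | 30 |
| 7 | 23 |
| 14 | 16 |
| 21 | 9 |
| 30 | 0 |

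**Patient who completes a cycle and then stops**
- Last venetoclax on cycle day 14: the window ends on cycle day 14 + 30 = 44. With End of Study on cycle day 28, the open part is 44 − 28 = 16 days.
- Last treatment is DLI on cycle day 15 (assuming DLI counts as study treatment): the window ends on cycle day 15 + 30 = 45. The open part is 45 − 28 = 17 days.

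**Patient who stops mid-cycle.** If the End of Study visit is held promptly, the open part approaches the full 30 days.

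**The two anchors differ.** Footnote c counts from discontinuing study drug; the AE window counts from the last dose. If discontinuation is dated to a decision on cycle day 28, the visit may be held as late as cycle day 28 + 30 = 58. That is 58 − 44 = 14 days after the window has closed, so the gap can be zero. The footnote's anchor is also unclear in another way: the synopsis names only venetoclax under study drugs, while responders continue azacitidine alone after cycle 12 (6.1).

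**Do other provisions close the gap?**
- Section 6.8 follows, where possible, patients who stop because of an AE. This concerns an existing event.
- Section 8.8 has a follow-up rule for patients who refuse the End of Study visit, limited to a related AE already present at the last visit.
- Section 8.9 allows unscheduled visits with AE monitoring, at the patient's request or the investigator's judgement.
- Sections 13.2 and 13.8 require prompt SAE reporting, which works once the site knows of the event.

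None of these systematically detects a new event starting between an early End of Study visit and day 30.

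**The case against.** The strongest reply is that nothing here is contradictory and little is lost. An End of Study visit on day 30 satisfies every provision. The duty to record AEs runs to day 30 whenever that visit takes place, and section 13.1 covers events the investigator observes as well as those the patient reports. SAEs must be reported, related events after day 30 are still recorded, and ongoing serious or grade 3 or higher events are followed. Most of this stands, and it limits the point to the absence of a scheduled assessment.

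A reader might infer three stronger things that the documents do not support:

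- **That part of the window is unobserved and the toxicity profile is therefore understated.** The recording duties above contradict the first part. Under 8.11, unrelated non-serious events below grade 3 would not enter the eCRF in any case. An infection needing hospitalisation is an SAE under 13.2. Understatement is possible but not shown.
- **That half the window is lost on average.** That figure (15 of 30 days) needs visits spread uniformly over days 0 to 30. The protocol gives no visit-timing distribution, and nothing in it shows that patients stopping for toxicity attend especially early. Only the range of 0 to 30 days is supported.
- **That dose escalation is compromised.** Dose-limiting toxicity is judged in Cycle 1, which has five scheduled AE assessments, and neutrophil recovery is judged up to day 42 (6.2). A gap after a patient's final course barely reaches this, although 6.2 does allow later AEs to be considered in escalation decisions.

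What the reply does not answer is that a fully compliant site may ask its last scheduled AE question before the window ends.

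**Conclusion.** The point holds as a gap in scheduled ascertainment. Depending on when the End of Study visit is held, 0 to 30 days of the post-treatment AE window have no scheduled assessment, with 16 days in the worked day-28 example. The gap is permitted rather than certain, and it disappears if the visit falls on or after day 30 from the last dose.

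The likely loss is confined to new-onset events in the open days that the site does not otherwise learn of. These are mainly non-serious related AEs of any grade and non-serious grade 3 or higher AEs. The two-stage efficacy decision is unaffected, and the Cycle 1 dose-limiting toxicity assessment is largely untouched.

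The conclusion rests on reading section 8.7 as the full list of data gathered at the 3- and 6-month contacts, and on Appendix 1 as the full list of scheduled AE assessments. It is a worthwhile, inexpensive correction to safety data collection and does not threaten the trial's main conclusions.

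**What to change.** 1. Reconcile the two time anchors, so that footnote c and sections 8.11, 13.1 and 13.2 count from the same defined event, and state which trial treatments that event refers to.
2. Add to footnote c that AE ascertainment closes no earlier than day 30 after the last dose of trial treatment. The End of Study marrow and laboratory tests can stay where they are.
3. Add to the 8.7 list that, where the End of Study visit was earlier, AEs with onset up to day 30 are recorded at the existing 3-month contact.

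The cost is a few lines of text and a few eCRF entries, with no new visit or procedure. The drawback is some recall error at 3 months. No dose or treatment rule changes.
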